### 5 STATISTICAL ANALYSES

### **5.1 DATA ANALYTIC PLAN**

Feasibility will be defined by our ability to meet our recruitment targets (56 people), frequency of engagement in the intervention by participants (group attendance and activity tracking/home-based adherence), and feedback on the intervention from participants. Feedback from participants will be incorporated into modifying the manual for the RCT and/or future interventions.

Analyses of intermediate and primary outcomes will primarily be descriptive in nature. We will calculate means, standard deviations, and within-group effect sizes of intermediate targets (SDT needs and autonomous motivation), proximal outcomes, including minutes spent walking, and steps/day, the primary outcome of CRF, and the secondary outcomes including RHR, blood pressure, loneliness, and symptoms. Further, we will calculate the percentage of the sample meeting the threshold for clinically significant changes in our outcomes of 6MWT, steps/day, and minutes spent walking to determine whether these changes are clinically meaningful. Finally, we will explore the relationship between baseline IQ, treatment adherence and outcome improvement so as to determine if cognitive functioning is associated with treatment response.

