### **PROTOCOL SYNOPSIS**

Study Title	Targeting Physical Health in Schizophrenia: Physical Activity Can Enhance life (PACE-Life)		
Funder	National Institutes of Mental Health		
Clinical Phase	Phase II		
Study Rationale	The purpose of the PACE-Life trial is to develop and test the feasibility of an exercise intervention that combines group walking, activity tracking, and heart rate monitoring, and determine the effectiveness of this intervention on the physical and mental health for individuals with schizophrenia spectrum disorders.		
Study Objective(s)	
 
Feasibility- Can PACE-life be delivered within this treatment setting?
 
Tolerability- How well is PACE-life accepted by the subjects?
 
Intervention adherence
 
Evaluation of PACE-life
 
		
Test Article(s) (If Applicable)	Fitbits Charge 3 devices, worn on the wrist, will be utilized to track daily steps, minutes spent walking, and monitor HR throughout exercise sessions. These devices will also be used to facilitate the		
Study Design	individualized/home-based component and goal-setting.  This is a two arm (fitbit only vs. fitbit + exercise intervention group), randomized controlled trial with 56 subjects (multiple groups occurring consecutively ranging from 13-18 participants).		
Subject Population key criteria for Inclusion and Exclusion:	
 
Inclusion Criteria
 
DSM-V diagnosis of a SSD (Schizophrenia, Schizoaffective Disorder, Brief Psychotic Disorder, Schizophreniform Disorder, and Unspecified Schizophrenia Spectrum and Other Psychotic Disorder)
 
Between the ages of 18-65, both genders, and any ancestry;
 
IQ>70 and/or reading level at, or above the 4th grade. IQ will be assessed using the Wechsler Abbreviated Scale of Intelligence (WASI) and the Wide Range Achievement Test (WRAT).
 
No hospitalizations for psychiatric reasons in the last 3 months
 
Clinically stable (no psychiatric medication changes within the past month)
 
Are not already engaging in consistent moderate-intensity exercise (cutoff = 60 min/week for the past 6 months);
 
		

- 7. Present with no contra-indication to engage in regular moderate intensity exercise based on the American College of Sports Medicine guidelines. (If an individual answers yes to one item on the of the Physical Activity Readiness Questionnaire (PAR-Q), she/he will be asked to get clearance from a physician prior to participating in the study)

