### Statistical And Analytic Plan

Analyses will primarily be descriptive in nature. We will calculate means, standard deviations, and within-group effect sizes of the primary outcome (CRF) and secondary outcomes (Ioneliness, symptoms, weight, BMI, waist circumference, resting heart rate, and blood pressure). Additionally, we will examine means, standard deviations, and within-group effect sizes of intermediate targets (self-determination basic needs and autonomous motivation) and proximal outcomes (minutes spent walking and daily steps).

DATA AND SAFETY	[name] will function as the Project Medical Officer. An
MONITORING PLAN	independent physician will serve as the Medical Monitor ([name]
	[name], from the Department of Psychiatry).

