### 3.1 OUTCOMES

The central hypothesis is that an intervention that increases physical activity as measured by minutes spent walking (at the prescribed intensity) and steps/day will result in improved health and lowered risk for premature mortality as evidenced by superior CRF (primary outcome), and on a variety of secondary outcomes (e.g. blood pressure). Guided by strong preliminary data and grounded in SDT, this hypothesis will be tested via three specific aims:

- 1. To develop a manual-based walking intervention for individuals with SSDs: PACE-Life. The manual will include guidelines for goal setting and translating intentions into behaviors (i.e., "if-then" plans), instructions for the group-based walking activity and home-based walking activity (which includes Fitbits), and increasing exercise intensity in a step-wise manner.
- 2. To examine the feasibility of implementing PACE-life at a community mental health clinic, and in a home-based virtual capacity, in a randomized controlled trial of 56 individuals with SSDs.
- 3. We will also examine the impact of PACE-life on intermediate targets (autonomous motivation and SDT needs), proximal outcomes (minutes spent walking and steps/day), the primary outcome of CRF, and secondary outcomes.

We hypothesize that PACE-life will be associated with:

- Improved proximal and primary outcomes including greater minutes/week spent walking and steps/day and increased CRF at mid-treatment (3 months), post-test (6 months), and one-month follow-up;
- Decreases in secondary outcomes including loneliness, SSD symptoms, resting heart rate, and blood pressure at mid-point, post-test, and one-month follow-up.
- Higher levels of theoretically-relevant, intermediate targets (autonomous motivation and SDT needs) at mid-treatment, post-test, and one-month follow-up.

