### 4 STUDY DESIGN

During this phase of the trial, 56 subjects will be assigned to the fitbit only group (control) or the PACE-Life walking group (intervention). The exercise intervention, PACE-Life, will last for 16 weeks and includes both group walks and independent walks (done at a location of the subject's choosing). Subjects will be asked to complete a total of 5 in-person, or virtual assessments at screening, baseline, mid-point, post-test, and 1-month follow-up.

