### **5.2 POWER ANALYSIS**

Power was estimated using Optimal Design Software. Assuming n=56 (28 per group), alpha=05, and the covariate accounted for 50% of variance, the proposed study has reasonable power to detect an effect size of .50 or larger in comparison of the groups at the end of treatment or follow-up and of .75 or larger in comparisons of the size of change over time. Thus, this study has good power to detect the types of differences detected in pilot study (ES of .50-1.03 in steps, .33-.40 in six-minute walk test, .54-.83 for BP and .52-1.09 for symptoms).

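### The outcome analysis is written as within-group effect sizes; the covariate-adjusted PACE-Life versus Fitbit-only comparison assumed in section 5.2 is never specified

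*Combined protocol and SAP*

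**What the plan says.** Section 5.1 states the general approach: "Analyses of intermediate and primary outcomes will primarily be descriptive in nature". It then lists the output: "We will calculate means, standard deviations, and within-group effect sizes of intermediate targets (SDT needs and autonomous motivation), proximal outcomes", continuing through the primary outcome of CRF and the secondary outcomes. The synopsis (Statistical And Analytic Plan) matches it: "We will calculate means, standard deviations, and within-group effect sizes of the primary outcome (CRF"), followed by the secondary outcomes. Section 5.1 adds a responder summary, "we will calculate the percentage of the sample meeting the threshold for clinically significant changes", which is not stated by arm, and an exploration of baseline IQ, adherence and improvement.

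The rest of the protocol sets up a comparison:

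- The synopsis gives a two-arm randomised design, and its Study Rationale includes the aim to "determine the effectiveness of this intervention on the physical and mental health for individuals with schizophrenia spectrum disorders".
- Section 4: "56 subjects will be assigned to the fitbit only group (control) or the PACE-Life walking group (intervention").
- Section 3.1 states a central hypothesis of improved health "as evidenced by superior CRF (primary outcome), and on a variety of secondary outcomes".
- Section 5.2 assumes 28 per group, alpha .05 and that "the covariate accounted for 50% of variance". It reports detectable effects of .50 for comparing the groups at end of treatment or follow-up, and .75 for comparing change over time.

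The covariate in section 5.2 is not named. Section 2.2 lists variables for possible use as covariates but gives no model.

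**The concern.** The control arm is there to remove whatever both arms share. Section 4.1.2 gives every subject a Fitbit, and the Background cites a review in which pedometer use raised activity by 26.9% over baseline. The protocol's own rationale therefore predicts some improvement in the control arm. A within-group effect size in the PACE-Life arm combines the programme's effect with the Fitbit effect, familiarity with the walk test on repetition, and time trends. Setting two within-group effect sizes side by side gives no valid estimate of the difference between arms and no measure of its uncertainty.

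At stake is the trial's only randomised evidence on its primary outcome. With no model, covariate, time point or analysis population written down, any comparison made later would rest on choices open after the data are seen.

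**Working it through.** **1. Inputs.** From section 5.2: 28 per arm, alpha .05 (two-sided assumed, since sidedness is not stated), covariate R² = .50, effect sizes .50 and .75, and a pilot six-minute walk effect of .33 to .40. All effects are in SD units. Assumptions not in the documents: 22 completers per arm (about 20% dropout), PACE-Life walking groups of 8 with ICC .05 to .10, and baseline-to-follow-up correlation r of .5 to .71.

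**2. What section 5.2 implies.** It gives power only in words, so there is no figure to match exactly. For a two-group comparison the noncentrality is d × √(n/2) / √(1 − R²).

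- d = .50, R² = .50: .50 × √14 / √.5 = 2.65; power 74% (noncentral t, 53 df).
- d = .50, no covariate: .50 × √14 = 1.87; power 45% (54 df).
- d = .75, no covariate: .75 × √14 = 2.81; power 79%.

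The .50 statement is credible only for a covariate-adjusted comparison between arms. A crude difference of the arm means that section 5.1 would report is a different and weaker analysis.

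**3. What the written output shows under no effect.** Suppose both arms improve by the same d of 0.33 to 0.40 SD. The PACE-Life within-group change then averages 0.33 to 0.40 SD, while the arm difference is d − d = 0. The size is assumed; the identity holds for any shared improvement.

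As an illustration only, because the plan states no within-arm test, suppose each arm were tested with a paired t-test at two-sided .05, with change SD = √(2(1 − r)). The chance that PACE-Life alone shows a significant improvement is about 18% to 25% with 28 per arm and 22% to 25% with 22 per arm (40,000 simulated trials per scenario). This is essentially p(1 − p), where p is the power within one arm, so it cannot exceed about 25%.

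**4. Precision of the comparison that should be specified.** Half-width of the 95% CI = t × √[(1 − R²)(1/n₁ + 1/n₂)].

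| Scenario | Calculation | Half-width (SD) |
|---|---|---|
| Adjusted, 28/arm | 2.006 × √(.5 × 2/28) | 0.379 |
| Unadjusted, 28/arm | 2.005 × √(2/28) | 0.536 |
| Adjusted, 22/arm | 2.020 × √(.5 × 2/22) | 0.431 |
| Adjusted, groups of 8, ICC .05 | 2.006 × √(.5 × (1.35 + 1)/28) | 0.411 |
| Adjusted, groups of 8, ICC .10 | 2.006 × √(.5 × (1.70 + 1)/28) | 0.440 |

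The design effect 1 + 7 × ICC is applied to the PACE-Life arm only.

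**5. Power of that comparison** (R² = .50, two-sided .05, noncentral t):

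| Effect size | 28/arm | 22/arm |
|---|---|---|
| .33 | 40% | 33% |
| .40 | 55% | 45% |
| .50 | 74% | 63% |

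Section 5.2 does not say whether the pilot values of .33 to .40 are between-arm or within-group effects. The first two rows apply to this trial only if they are between-arm.

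**The case against.** The strongest reply is that this is an early-stage trial. Three of its four listed objectives are feasibility, tolerability and adherence; the aim in section 3.1 that names the randomised trial is a feasibility aim; and a descriptive emphasis suits such a study. The word primarily in section 5.1 leaves room for other analyses, and arm means and SDs allow a reader to form a difference. Section 5.2 takes n=56 as given and reports detectable effects, so it supports that number without deriving it. Superior CRF in section 3.1 names no comparator, and the hypotheses listed below it could be read as change over time. Section 5.1 may also carry over text from the single-arm open trial, where within-group effect sizes are appropriate.

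Much of this is fair. The feasibility analyses need no change, and the gap may well be a drafting omission. But nothing comparative is specified under that word, and the difference readers could form is unadjusted. Aim 3 is to examine the impact on CRF, and in a randomised design with a named control that means impact against the control. Dropping the effectiveness wording and the power statement would remove the inconsistency, but would leave the randomised control unused for efficacy.

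It is also true that the dropout, clustering and correlation values above are assumptions, and that the illustration in step 3 models tests the plan does not propose. The conclusion does not depend on them.

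**Conclusion.** The concern holds and must be fixed. The output named in section 5.1 and the synopsis cannot isolate PACE-Life's effect over Fitbit only, and it does not match the analysis assumed in section 5.2. The bias from reading the PACE-Life within-group effect as the programme's effect equals whatever improvement the arms share: 0.33 to 0.40 SD under the assumed scenario. That finding follows from the text and the design alone.

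The correct comparison will be imprecise. Its half-width is about 0.38 SD on section 5.2's assumptions, and 0.41 to 0.44 SD with the assumed dropout or clustering, each taken separately. Power is about 40% to 55% at .33 to .40 with full follow-up. This calls for cautious labelling of the efficacy result; it does not justify leaving the comparison out.

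**What to change.** Reconcile section 5.1 and the synopsis with section 5.2:

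- Define the efficacy estimate as the between-arm difference in six-minute walk distance at one named time point, adjusted for baseline distance, with a 95% CI. Section 5.2 allows end of treatment or follow-up; choose one (end of treatment is the natural candidate). Section 3.1 puts post-test at 6 months, while the synopsis and section 4 describe 4 months or 16 weeks of intervention, so those passages must be reconciled first.
- Analyse all randomised participants in their assigned arm and state how missing distances are handled.
- Use the same model for the other outcomes, labelled exploratory.
- Report the percentages with clinically significant change by arm, with their difference and CI.
- Keep within-group effect sizes as supporting description.
- Name the covariate in section 5.2 and label the efficacy results preliminary.

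The cost is a few sentences in section 5.1, section 5.2 and the synopsis and a few lines of code. The assessments in section 4.2.2 already include the six-minute walk at baseline, mid-point, post-test and follow-up, so no new visits or participants are needed. The feasibility analyses are unchanged.

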### **5.2 POWER ANALYSIS**

Power was estimated using Optimal Design Software. Assuming n=56 (28 per group), alpha=05, and the covariate accounted for 50% of variance, the proposed study has reasonable power to detect an effect size of .50 or larger in comparison of the groups at the end of treatment or follow-up and of .75 or larger in comparisons of the size of change over time. Thus, this study has good power to detect the types of differences detected in pilot study (ES of .50-1.03 in steps, .33-.40 in six-minute walk test, .54-.83 for BP and .52-1.09 for symptoms).

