### **Efficacy Evaluations**

Primary outcome- 6MWT will be used to measure CRF during which individuals will be asked to walk continuously for six minutes on a flat, indoor surface around cones (separated by 100ft). Supplemental CRF measures will also be used. CRF will be calculated using an equation by Jackson, A. S., et al. 1990 that includes recent weight and height for the calculation of BMI, gender, self-reported physical activity level, and age. Finally, participants will complete the Chair-Rise Task, and the 2-minute Step Test to measure CRF.

Secondary outcomes- Psychological- UCLA Loneliness Scale will be used to assess subjective feelings of loneliness. The PANSS will be utilized to assess psychiatric symptoms.

Secondary outcomes- Biological- We will measure weight, BMI, and waist circumference at all in-person assessments. We will examine these characteristics to determine if they changed as a result of increasing exercise. Resting Systolic/Diastolic Blood Pressure and RHR will also be assessed following standardized procedures.

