### 4.2.2 BASELINE, MID-POINT, POST-TEST, 1 MONTH FOLLOW-UP

The following measures will be examined at the baseline, mid-point, post-test, and 1 month follow-up study visits:

- Demographics- We will collect information on age, sex, ancestry, education, parent education, smoking, substance use, current medications, duration of outpatient treatment, and diet.
- Minutes Spent Walking- We will utilize data recorded from Fitbits to assess minutes spent
  walking (by syncing Fitbits to corresponding Fitbit.com accounts and loading deidentified data
  onto study laptops).

- The Short Form International Physical Activity Questionnaire (IPAQ), a valid self-report
  measure, to assess changes in physical activity. The IPAQ Short Form is a four-item scale that
  assesses frequency and duration of walking, moderate-intensity exercise, vigorous-activity
  exercise, and sitting.
- Steps/day. We will also collect daily step numbers using Fitbit data downloaded onto study laptops from Fitbit.com at group sessions.
- Cardiorespiratory fitness (CRF)- CRF will be measured using the 6-minute walk test (6MWT) during which individuals are asked to walk continuously for six minutes on a flat, indoor surface around cones (separated by 100ft) and the primary outcome is the total distance walked. The 6MWT is recommended for use with sedentary individuals and to evaluate the impact of an exercise intervention. Moreover, the 6MWT has been successfully administered to individuals with SSDs, including those in our pilot trial. As a result, we plan to utilize the 6MWT as our primary measure of CRF. Supplemental CRF measures will also be used. CRF will be calculated using an equation by Jackson, A. S., et al. 1990 (119) that includes recent weight and height for the calculation of BMI, gender, self-reported physical activity level, and age. Finally, participants will complete a Chair-Rise Task, where subjects will sit and stand from a chair for 30 seconds, and the 2-minute Step Test, where subjects will walk in place with their knees raising to hipheight, to measure CRF.

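### Section 5.2 concludes that power is good for the pilot effects, but the pilot effect on the primary measure, the 6MWT (.33-.40), lies wholly below both detectable effects (.50 and .75) stated one sentence earlier

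*Combined protocol and SAP*

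**What the plan says.** Section 5.2 (Power Analysis) sets its inputs as "Assuming n=56 (28 per group), alpha=05, and the covariate accounted for 50% of variance". It claims "reasonable power to detect an effect size of .50 or larger in comparison of the groups at the end of treatment or follow-up". A second, higher limit of .75 is given for comparing how much participants change. No numerical power is attached to either limit.

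The next sentence reads "Thus, this study has good power to detect the types of differences detected in pilot study" and lists those differences in brackets: "ES of .50-1.03 in steps, .33-.40 in six-minute walk test, .54-.83 for BP and .52-1.09 for symptoms".

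The 6MWT is the primary measure. Section 4.2.2 says "we plan to utilize the 6MWT as our primary measure of CRF", and the synopsis (Efficacy Evaluations) places it under the primary outcome: "6MWT will be used to measure CRF during which individuals will be asked to walk continuously for six minutes". Section 3.1 hypothesises superior cardiorespiratory fitness as the primary outcome.

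Section 5.2 does not say whether alpha is one- or two-sided, whether the pilot effects are between-group or within-group, or which standard deviation they are scaled by.

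**The concern.** The last sentence of section 5.2 is presented as following from the limits before it. For the 6MWT it contradicts them: the largest pilot value, .40, is below the smaller limit, .50. The wording also moves from reasonable power to good power with nothing in between to justify the step.

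The 6MWT is the only listed outcome whose entire pilot range misses both limits, and it is the primary one. A reader who relies on the sentence would expect the trial to pick up a pilot-sized 6MWT difference, and could take a non-significant result as evidence of no effect.

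**Working it through.** **1. Printed numbers side by side (no calculation needed)**

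| Outcome | Pilot effect | Against .50 (groups) | Against .75 (change) |
|---|---|---|---|
| 6MWT | .33-.40 | all below | all below |
| Steps | .50-1.03 | all at or above | low end below |
| Blood pressure | .54-.83 | all above | low end below |
| Symptoms | .52-1.09 | all above | low end below |

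**2. Do the stated limits fit the stated inputs?**

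Inputs from section 5.2: n = 28 per group, alpha .05 (printed without its decimal point), R² = .50. Sidedness is not given, so both are shown. Power comes from the noncentral t distribution.

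- Group comparison with covariate: noncentrality = d/√(1 − R²) × √(n/2) = d/√.5 × √14 = 5.292d, with 53 df. At d = .50 this is 2.646, and power is 73.8% two-sided or 83.3% one-sided. Power of 80% is reached at d = .539 two-sided or .476 one-sided.
- Change limit, read as a between-group comparison without covariate gain (assumption): noncentrality = d × √14 = 3.742d, with 54 df. At d = .75 this is 2.806, and power is 78.7% two-sided or 87.0% one-sided.

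Both limits are therefore credible at a power of roughly 75-80% two-sided. The fault lies in the conclusion drawn from them.

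**3. 6MWT, pilot effects read as between-group SDs (assumption)**

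With R² = .50 and all 28 per group retained:

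- d = .33: noncentrality 5.292 × .33 = 1.746; power 40.3% two-sided, 53.1% one-sided.
- d = .40: noncentrality 5.292 × .40 = 2.117; power 54.7% two-sided, 67.2% one-sided.

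Without the covariate the two-sided figures are 22.8% and 31.2%. Section 5.2 makes no allowance for dropout. If 22 per group remained (assumption), the two-sided range with R² = .50 would be about 33-45%.

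**4. 6MWT, pilot effects read as within-group (assumption), paired test in one arm of 28, 27 df**

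- In SD-of-change units: noncentrality = d × √28, again 1.746 and 2.117; power 39.1% and 53.2% two-sided (52.3% and 66.2% one-sided).
- In raw-SD units: the effect is first divided by √(2(1 − r)), where r is the pre-post correlation. The documents give no r. If the covariate is the baseline value and R² = .50, then r = √.50 = .71 (assumption). The divisor is .765, the effects become .431 and .523, and power is 59.5% and 76.0% two-sided (71.9% and 85.3% one-sided). Two-sided power of 80% needs r of about .73 at .40 and .82 at .33.

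**5. Low ends of the other outcomes, read as between-group**

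With R² = .50: .50 gives 73.8%, .52 gives 77.1% and .54 gives 80.1% two-sided. That suits the word reasonable for the group comparison. Under the no-covariate reading of the change limit, the same values give 45.1%, 48.1% and 51.0%.

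**The case against.** The strongest reply is that the comparison may not be like for like. Section 5.1 and the synopsis plan within-group effect sizes, so the pilot figures may be within-group too. On one such reading (raw-SD units, r = .71, one-sided) an effect of .40 has 85% power, which many would call good. This point stands in part: 40-55% cannot be asserted as the trial's power without knowing the metric. It does not rescue the sentence. Within-group effects do not map onto limits for comparing groups, so the inference would then rest on nothing. The favourable figures also need a correlation and a sidedness that the plan does not state, and they describe change in one arm, not the randomised comparison.

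The second reply is that little hangs on the sentence. Section 2.1 describes a small-scale randomised trial, section 5.1 and the synopsis call for mainly descriptive analyses, and no between-group test of the 6MWT is specified. This also stands, and it limits the consequence. It does not make the statement correct, since section 5.2 chose to make a claim about power.

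A reader might go further and infer that the sample size is wrong, or that the limits were miscalculated. The documents support neither. Low power for the primary measure is acceptable at this stage if it is described as such, feasibility is defined in section 5.1 by recruitment, engagement and feedback, and both limits are roughly reproduced from the stated inputs.

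**Conclusion.** The concern holds as an internal inconsistency in the stated power. As printed, the whole 6MWT range is below both limits, and nothing elsewhere restricts or explains the good-power claim. That conclusion needs no assumption.

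Its size is conditional. Between-group reading, 28 per group, R² = .50, full retention: about 40-55% two-sided, 53-67% one-sided. Within-group reading: about 39-53% two-sided in SD-of-change units, or 60-76% two-sided in raw-SD units if r = .71.

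It would be too strong to say the sentence fails for every outcome. If the pilot effects are between-group, steps, blood pressure and symptoms meet the .50 limit across their ranges; only their low ends (.50-.54) miss the .75 limit for change. The error should be corrected because it concerns the primary measure, but it alters no sample size, analysis or decision rule.

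**What to change.** 1. State in section 5.2 whether alpha is one- or two-sided, and whether the pilot effects are between-group or within-group and in which SD. This comes first, because the remaining wording depends on it.
2. Take the 6MWT out of the good-power sentence. Say that the trial does not have good power for a 6MWT effect of .33-.40, and give the single power figure that matches the stated metric, with its assumptions (28 per group or per arm, R² or pre-post correlation, retention). If the effects are within-group, say that the figure refers to change in one arm.
3. For steps, blood pressure and symptoms, claim only reasonable power for the end-of-treatment group comparison, and only if the pilot effects are between-group. Add that the low ends of their ranges (.50-.54) are below the .75 limit for change.

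The cost is one reworded sentence and a few stated facts. The declared power for the primary measure becomes less favourable. No extra participants and no new analyses are needed.
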